3.0 INVESTIGATIONAL PLAN

3.1 Study Design

This is a Phase 3, prospective, randomized, double-masked, two-arm, multi-center study evaluating the efficacy and safety of repeated dosing of KSI-301 5 mg administered by intravitreal injections in participants with treatment-naïve NPDR. A brief description of the study design and study treatment regimen appears below; additional details can be found in the study protocol.

The schedules of activities are provided in Appendix 1 (SoA-A and SoA-B).

The overall duration of the study was intended to be approximately 2 years (100 weeks) after the last participant is randomized to the study. Participant duration is defined as the date a signed written informed consent is provided through the last safety follow-up visit at Week 100; thus, the maximum participant duration is approximately 103 weeks and includes a screening period of up to 21 days (Days -21 to -1), a treatment period of approximately 92 weeks (Day 1 to Week 92), a safety/efficacy assessment at Week 96, and a final follow-up for safety assessments at Week 100 . The primary endpoint will be assessed at Week 48; although secondary endpoints for efficacy were intended to be assessed at Weeks 48 and 96, the Sponsor has made a decision as of late July 2023 to discontinue further development of KSI-301, and therefore data collected after Week 48 will be incomplete.

A single eye per participant will be designated as the Study Eye. If both eyes are eligible to become the Study Eye, the eye with worse BCVA and/or worse DR severity at Screening will be selected as the Study Eye. If both eyes are eligible and have the same BCVA and/or DR severity or one eye has worse BCVA and the fellow eye has worse DR, the decision of which eye to select as the Study Eye will be made by the Investigator.

Participants will be randomly assigned (1:1) into one of two treatment arms:

- Group A: KSI-301 5 mg via intravitreal injection at Day 1, Week 8, Week 20, and every 24 weeks thereafter through Week 92.
- Group B: Sham injection at Day 1, Week 8, Week 20, and every 24 weeks thereafter through Week 92.

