5.8 Analysis Visit

For efficacy analyses, unscheduled or early termination visits will be assigned a study day and then mapped to the appropriate analysis window as detailed in Table 3. In the event where more than one record falls in the same analysis window, the following rules will be used in sequential order to determine the record that will be used for data analysis:

- If there is a scheduled visit (including scheduled visits from SoA-B in Appendix 1) in the analysis window, then the scheduled visit's data will be used.
- If there is no scheduled visit in the analysis visit window, the record (including records from SoA-B in Appendix 1) that is the closest to the scheduled study day at a given visit will be used.
- If there is no scheduled visit in the analysis visit window and there is a tie between the two records with regards to the number of days before and after the scheduled study day, the later record will be used.

Analysis visit windows will not apply to subject data listings. Prior to any missing data imputations or analysis, the analysis visit windows will be applied to the data.

Nominal Visit	Scheduled Study Day	Starting Day for Nominal Visit	Ending Day for Nominal Visit
Day 1	1	1	1
Week 8	56	2	98
Week 20	140	99	182
Week 32	224	183	266
Week 44	308	267	322
Week 48	336	323	364
Week 56	392	365	434
Week 68	476	435	518
Week 80	560	519	602
Week 92	644	603	658
Week 96	672	659	686

Table 3: Windows for Unscheduled Visit

Note: Nominal visits for efficacy assessments are at Day 1, Week 8, every 12 weeks from Week 20 – Week 44, Week 48, every 12 weeks from Week 56 – Week 92, and Week 96.

6.0 **BASELINE ANALYSES**

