7.3 Additional Secondary Efficacy Analyses

As specified in Section 4.0, the Primary Analysis will evaluate the efficacy of KSI-301 compared to sham from Day 1 up to Week 48.

Table 4 lists the additional secondary efficacy endpoints, efficacy variable derivations, reporting statistics and analysis methods for the Primary Analysis and until the end of study.

Binary secondary efficacy endpoints will utilize the Cochran-Mantel-Haenszel (CMH) method stratified by the randomization stratification factors (i.e. baseline DRSS level and HbA1c level).

Time to event endpoints will be analyzed using the Kaplan-Meier estimates. The number of observations censored will be provided for each treatment group. The 50th percentile of Kaplan-Meier estimates will be used to estimate the median time to first event in each treatment group. A 2-sided 95% CI will be provided for the estimates. A log-rank test stratified by the randomization stratification factors (i.e. baseline DRSS level and HbA1c level) will be performed to compare the survival distributions between the treatments. The hazard ratio and its 95% CI will be reported from a Cox regression model stratified by the same randomization stratification factors with treatment as the covariate. For patients not known to have had an event at the time of the analysis data cutoff, the time will be censored at the date of the last scheduled study visit at analysis data cutoff.

Continuous endpoints (e.g. mean change from baseline in BCVA) will utilize a Mixed Model for Repeated Measures (MMRM). The model assumes missing at random (MAR). The model will include the change from baseline value as the dependent variable; categorical covariates of treatment group, protocol scheduled visit, treatment × visit interaction, and the randomization stratification factors (i.e. baseline DRSS level and HbA1c level) as well as continuous covariate of baseline BCVA, as fixed effects; and then subject as a random effect. Within-subject correlations will be assumed to follow an unstructured covariance matrix. If the model assuming an unstructured covariance matrix does not converge, a heterogeneous compound symmetry structure or an AR(1) covariance structure will be fitted.

For all additional secondary efficacy endpoints, data after the occurrence of intercurrent event will be censored, and missing and non-gradable data will not be imputed. Only observed, gradable and non-censored data will be used for analysis.

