of AEs] Time to first development of DME through Week 48 Time from first treatment to development of DME (in months) [Sight-threatening Complication/EDC]						
Mean change in SD-OCT central subfield thickness (CST) from baseline by visit over time	Continuous Endpoint: Change from baseline to each time point	LS Mean difference in change from baseline to each time point and 95% CI [FAS], up to Week 48 [FAS], up to end of study	MMRM (Section 7.3) adjusting for baseline CST, with time, treatment, and time*treatment interaction and randomization stratification as factors Unstructured covariance matrix			
Mean change in BCVA from baseline by visit over time	Continuous Endpoint: Change from baseline to each time point [Visual Acuity Score/EDC]	LS Mean difference in change from baseline to each time point and 95% CI [FAS], up to Week 48 [FAS], up to end of study	MMRM (Section 7.3) adjusting for baseline BCVA, with time, treatment, and time*treatment interaction and randomization stratification as factors Unstructured covariance matrix			

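### The SAP's MMRM adds a redundant random subject effect to an unstructured covariance, and its unordered fallback allows a homogeneous AR(1) that can misstate Week 48 standard errors

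*SAP*

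**What the plan says.** SAP section 7.3 describes the MMRM for continuous additional secondary endpoints. After the fixed effects it adds "and then subject as a random effect. Within-subject correlations will be assumed to follow an unstructured covariance matrix". The next step is conditional: "If the model assuming an unstructured covariance matrix does not converge, a heterogeneous compound symmetry structure or an AR(1) covariance structure will be fitted". The section states no order between the two fallback structures, no selection criterion, no robust standard error and no degrees-of-freedom method.

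Table 4 in the same section points back to 7.3 but describes the BCVA model as "adjusting for baseline BCVA, with time, treatment, and time*treatment interaction and randomization stratification as factors Unstructured covariance matrix". The CST row reads the same way with baseline CST. Neither row has a random subject effect or a fallback. Both endpoints are to be analysed up to Week 48 and up to end of study.

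Three other statements bear on the point. On the visit grid, SAP section 5.8 says "Nominal visits for efficacy assessments are at Day 1, Week 8, every 12 weeks from Week 20", and its Table 3 shows visits at Weeks 8, 20, 32, 44 and 48, then 56, 68, 80, 92 and 96. On missing data, 7.3 says "The model assumes missing at random (MAR") and that "data after the occurrence of intercurrent event will be censored, and missing and non-gradable data will not be imputed". On Year 2, section 3.1 says "therefore data collected after Week 48 will be incomplete".

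The SAP contents list sample MMRM code in Appendix 2, but that code is not in the text available, so the intended implementation cannot be checked.

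**The concern.** There are two linked problems. First, an unstructured residual matrix already contains any variance that a random subject intercept could explain. Section 7.3 therefore carries one covariance parameter too many and disagrees with Table 4, and two programmers could fit different models from the same SAP.

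Second, a redundant variance parameter can contribute to a singular Hessian or a failed fit, and a failed fit is what triggers the fallback. The choice between the two fallback structures is then open after unmasking. One of them, AR(1), imposes a single variance on every visit and treats the 4-week gap from Week 44 to Week 48 like the 12-week gaps before it. If it is used, the confidence intervals for BCVA and CST at Week 48 rest on the assumption that the unstructured matrix was meant to avoid. The missing order is a defect whatever causes the non-convergence.

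**Working it through.** The plan states no figure on this point, so there is none to reproduce.

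**Step 1: redundancy.** Inputs: T = 5 post-baseline visits to Week 48 and T = 10 to end of study (SAP section 5.8, Table 3). The marginal covariance is V = σ_b²·J + R, where J is a matrix of ones and R is unstructured. R has T(T+1)/2 parameters.

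| | R | R plus σ_b² | Rank of the map to V |
|---|---|---|---|
| T = 5 | 5×6/2 = 15 | 16 | 15 |
| T = 10 | 10×11/2 = 55 | 56 | 55 |

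One parameter is always redundant. On one simulated data set of 240 participants and five visits, the log-likelihood was −2298.36 at each of σ_b² = 0, 5, 10 and 15 with R adjusted to keep V fixed. Because V does not change, neither does the treatment contrast or its standard error. Only the split between σ_b² and R is undetermined.

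**Step 2: AR(1) at Week 48, closed form.** Inputs: 120 per arm (SAP section 9.0). The SDs are assumptions: 7.5 letters at Week 48, and 6, 5 or 4 at Week 8, linear in weeks between. With complete data, AR(1) uses roughly the average visit variance in place of the Week 48 variance (7.5² = 56.25):

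- ratio of model SE to true SE ≈ √(mean visit variance / 56.25)
- actual two-sided error rate = 2·[1 − Φ(1.96 × ratio)]

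| Week 8 SD | Variances at Weeks 8, 20, 32, 44, 48 | Mean | Ratio | Error rate |
|---|---|---|---|---|
| 6 | 36.0, 41.6, 47.6, 54.0, 56.25 | 47.1 | 0.915 | 7.3% |
| 5 | 25.0, 33.1, 42.25, 52.6, 56.25 | 41.8 | 0.862 | 9.1% |
| 4 | 16.0, 25.5, 37.2, 51.1, 56.25 | 37.2 | 0.813 | 11.1% |

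In the last row the true SE of the difference is √(2×56.25/120) = 0.97 letters, and AR(1) would report about √(2×37.2/120) = 0.79.

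**Step 3: best-fitting AR(1).** Fitting the closest (Kullback-Leibler) AR(1) under several assumed correlation patterns gives an SE that is too small by 9–10%, 14–16% and 19–21%, with error rates of 7.3–7.7%, 9.2–9.9% and 11.2–12.3%. The spread reflects the unknown path of the SD and the correlations.

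**Step 4: other directions and the other fallback.** These use the same method, with the SD linear by visit and a correlation of 0.4 + 0.6·exp(−gap in weeks/30). Each cell gives the ratio of model SE to true SE and the error rate.

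| SD path (letters) | AR(1), complete data | AR(1), 5% loss per visit |
|---|---|---|
| 5 to 9 | 0.80 (11.6%) | 0.79 (12.4%) |
| 6 to 8 | 0.88 (8.4%) | 0.88 (8.6%) |
| flat at 7 | 1.00 (5.0%) | 1.01 (4.8%) |
| 9 to 5 | 1.44 (0.5%) | 1.49 (0.4%) |

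Heterogeneous compound symmetry gives 1.00 with complete data and 0.986 (5.3%) with 5% loss per visit, in all four rows. The flat row shows that ignoring the short Week 44–48 gap does little by itself here. The equal-variance constraint drives the error.

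**Step 5: sandwich SE.** For the 5-to-9 path with complete data, AR(1) reports 0.93 letters. The sandwich formula recovers the true 1.16.

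**The case against.** The wording about a random subject effect may be loose language for the subject identifier in a repeated-measures model. Table 4 omits it, and the sample code that could settle the question is not available. This stands, and it is why the remedy starts with making 7.3 and Table 4 agree.

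A reader might infer that the model is unidentifiable and the treatment effect cannot be estimated. The algebra does not support that: the marginal covariance, the contrast and its standard error are all identified. A reader might also infer that the redundant term will cause non-convergence. No failed fit has been shown, and 15 parameters for about 240 participants is not demanding. The 55-parameter end-of-study model on incomplete data is the likelier place for a failure.

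It is also fair to say that the fallback is only partly at fault. Heterogeneous compound symmetry is named first and already keeps visit-specific variances. For wrong error bars, the fit must fail, the analyst must drop the unstructured matrix instead of the redundant term, and AR(1) must then be chosen. Even so, nothing in the text prevents that sequence, and the unordered choice remains open.

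**Conclusion.** The point holds as a specification fault with a limited consequence. The random intercept is redundant and conflicts with Table 4. The fallback rule is unordered, has no robust standard error, and admits a structure that can misstate precision.

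The size depends on SDs that the documents do not give. Under the assumed rise to 7.5 letters from 6, 5 or 4, the AR(1) Week 48 standard error is about 9% to 20% too small and the error rate about 7% to 12%. With a flat SD it is correct, and with a falling SD it is too large. It would be wrong to conclude that AR(1) always inflates the error rate, or that both fallbacks carry the same risk: heterogeneous compound symmetry is off by about 1%.

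Nor do the documents support extending this to the trial's main conclusions. The primary and key secondary endpoints are proportions analysed by CMH in a separate hierarchical family (SAP section 7.2). Only mean change in BCVA and CST is affected.

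**What to change.** In SAP section 7.3, delete the clause naming subject as a random factor, so that the text matches Table 4, and fit an unstructured residual matrix by visit within subject. Replace the open choice with a fixed order of structures that keep visit-specific variances, for example heterogeneous Toeplitz, then heterogeneous compound symmetry. Remove homogeneous AR(1). State that sandwich standard errors will be reported with any fallback structure.

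The cost is a short edit to one paragraph, with no new data. When the unstructured model converges, results do not change. There is a small downside: sandwich standard errors are slightly less stable in small samples. They also do not remove any bias in the mean difference that a wrong covariance can cause when data are missing at random, which was not quantified here.

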1.0 INTRODUCTION

The purpose of this statistical analysis plan (SAP) is to provide a comprehensive and detailed description of the methods and presentation of data analyses for Study KS301P106 (Protocol Amendment 1.1, dated 17 May 2021), entitled *A Prospective, Randomized, Double-masked, Sham-controlled, Multi-center, Two-arm, Phase 3 Study to Evaluate the Efficacy and Safety of Intravitreal KSI-301 in Participants with Moderately Severe to Severe Non-proliferative Diabetic Retinopathy (NPDR).* This study is conducted in accordance with the protocol, Good Clinical Practice, the Declaration of Helsinki, and any other applicable regulatory requirements.

Descriptions of planned analyses are provided *a priori* to preserve the validity of the interpretation of the statistical analysis results. The statistical methods applied in the design and planned analyses are consistent with the International Council for Harmonisation (ICH) guidelines *Statistical Principles for Clinical Trials* (E9) (1998) and ICH E9 (R1) *Addendum on Estimands and Sensitivity Analysis in Clinical Trials to the Guideline on Statistical Principles for Clinical Trials* (2020).

This SAP provides details of the statistical analysis results to be presented in the clinical study reports (CSR). Details about the unmasking plan for study treatment assignment, including the procedures and guidelines that Kodiak, study sites, and vendors will follow to ensure that masking of the study is appropriately maintained during the conduct of the study, will be detailed in a separate document. Analyses of pharmacokinetics, biomarkers, and anti-drug antibodies will be addressed in separate analysis plan(s).

Any changes between the statistical methods and study endpoints provided in the clinical study protocol and this SAP will be described and explained in Section 10.0; any changes or deviations from this SAP relative to the final analyses will be fully documented in the CSRs. Minor changes or deviations from the templates for tables, figures, and listings need not be documented in the CSRs.

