5.0 GENERAL STATISTICAL METHODS

SAS (SAS Institute Inc., Cary NC, USA) Version 9.4 or higher will be used for the study analyses.

5.1 **Reporting Conventions**

Tables and figures will be summarized by treatment group. Tables summarizing demographics and other baseline characteristics will also include a column for all patients combined. In general, all data collected and any derived data will be presented in subject data listings, for all randomized patients. Listings will be ordered by treatment group, subject number, and assessment or event date. The treatment groups will be displayed in the same order as the summary tables. The treatment groups presented in listings will be based on the planned assignment, unless otherwise noted.

In general, continuous variables will be summarized to indicate the study population sample size (N), number of subjects with available data (n), mean, SD, median, 25th (Q1) and 75th (Q3) quartiles, minimum, and maximum values. Categorical variables will be summarized by the population size (N), number of subjects with available data (n), number of subjects in each category, and the percentage of subjects in each category. Unless otherwise noted, the denominator to determine the percentage of subjects in each category will be based on the number of subjects with available data. The denominator for percentages for incidence data (such as adverse events) will be based on the number of subjects in the analysis population "at risk." Select ordinal data may be summarized using both descriptive statistics and counts and percentages of subjects in each category, as appropriate.

Non-zero percentages will be rounded to one decimal place. Percentages that round down to 0 or up to 100% will be displayed as "<0.1%" and ">99.9%", respectively. Rounding conventions for presentation of summary statistics will be based on the precision of the variable of summarization, as it is collected in its rawest form e.g., on the electronic case report form (eCRF) and are outlined as follows:

- The mean and median will be rounded to an additional decimal place than the precision of the variable of summarization;
- Measures of variability (e.g., SD, SE) will be rounded to two additional decimal places than the precision of the variable of summarization; and
- Minimum and maximum values will be presented using the same precision as the variable of summarization.

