7.1.1.4 Intercurrent Events

The following intercurrent events (ICEs) may impact the assessment of the primary efficacy endpoint:

- 1. Treatment misallocation at 1 or more study visits.
- 2. Use of prohibited medications in the study eye.
- 3. Development of sight-threatening complication(s) and initiation of open-label KSI-301 5 mg treatment, panretinal photocoagulation, or other treatment for DME, ASNV, and/or PDR.
- 4. Premature discontinuation from study treatment due to study eye adverse events or due to lack of efficacy.
- 5. Premature discontinuation from study treatment due to events unrelated to study treatment such as malignancies, systemic infections, trauma, or other systemic adverse events that are not treatment-related, including discontinuations due to COVID-19.

Intercurrent events will be classified by the Sponsor prior to treatment code unmasking to prevent potential bias. Intercurrent events and the time to intercurrent events will be tabulated and listed by treatment group. Strategies for addressing the potential impact of these intercurrent events are described below.

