7.1.2 Analysis of Primary Efficacy Endpoint

The primary efficacy endpoint will be estimated based on the FAS, i.e., all randomized subjects who received at least one treatment injection and have gradable DRSS value at baseline.

The statistical analysis will be performed using the Cochran-Mantel-Haenszel (CMH) method,

A 'Hypothetical' strategy will be applied for all intercurrent events where measurements after occurrence of intercurrent event will be imputed using the last observation carry forward (LOCF) procedure. For patients who develop sight-threatening complication(s) and have non-gradable value at their first visit where open-label treatment is administered, the non-gradable values will be imputed as no change from baseline. For patients without intercurrent event, missing and non-gradable values at Week 48 will be imputed using LOCF. Baseline will be carried forward if all post-baseline observations are missing or non-gradable. Non-gradable values are observations where DRSS level is 90.

The p-value will be reported for comparison between KSI-301 and sham groups. In addition, the weighted percentages difference between the KSI-301 and sham (i.e., KSI-301 – sham) and 95.02% CI of the difference will be presented. Percentages are calculated as 100×number of "responders"/number of patients in FAS. Weighted percentages are based on weighted average of observed estimates across strata using CMH weights. The CI are based on the normal approximation to the binomial proportions.

The CMH method as described for the primary efficacy analysis will be used for all sensitivity analyses below.

7.1.3 Sensitivity Analysis 1

In this analysis, a 'Composite' strategy will be applied for all intercurrent events where patients with occurrence of intercurrent event by Week 48 will be considered as non-responders. For patients without intercurrent event, missing and non-gradable values at Week 48 will be imputed using LOCF, and baseline will be carried forward if all post-baseline observations are missing or non-gradable as in the primary analysis.

7.1.4 Sensitivity Analysis 2

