7.2.1 Proportion of Eyes Developing Any Sight-Threatening Complication

The first key secondary efficacy endpoint of interest is the proportion of eyes developing any of the following from baseline through Week 48:

- PDR or ASNV;
- Vitreous hemorrhage or tractional retinal detachment believed to be due to PDR; or
- DME.

The development of the above sight-threatening complications is tabulated from adverse events, procedures and eCRFs.

The following intercurrent events will be evaluated in this key secondary endpoint:

- Treatment misallocation at 1 or more study visits.

- Use of prohibited medications in the study eye.

-Premature discontinuation from study treatment due to study eye adverse events or due to lack of efficacy.

-Premature discontinuation from study treatment due to events unrelated to study treatment such as malignancies, systemic infections, trauma, or other systemic adverse events that are not treatment-related, including discontinuations due to COVID-19.

The same analysis method from the primary efficacy endpoint will be used for the first key secondary efficacy endpoint. See Section 7.1.2.

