Additional Secondary Efficacy Endpoint	Variable Derivation [Source]	Summary Statistics [Analysis Set]	Method of Analysis		
Proportion of eyes developing PDR or ASNV from baseline through Week 48	Binary endpoint: patients developed PDR or ASNV (yes/no) [Sight-threatening Complication/EDC]				
Proportion of eyes developing vitreous hemorrhage or tractional retinal detachment, believed to be due to PDR, from baseline through Week 48	Binary endpoint: patients developed vitreous hemorrhage or tractional retinal detachment believed to be due to PDR (yes/no) [Sight-threatening Complication/EDC/Review of AEs]				
Proportion of eyes developing DME from baseline through Week 48	Binary endpoint: patients developed DME (yes/no) [Sight-threatening Complication/EDC]	Difference in proportions (%) and 95% CI at each time point [FAS], up to Week 48	CMH method adjusting for randomization stratification factors (similar to Section 7.1.2)		
Proportion of eyes with a ≥ 2 - step or a ≥ 3 -step worsening on DRSS from baseline at Week 48	Binary endpoints: patients with a ≥2-step worsening in DRSS (yes/no); patients with a ≥3-step worsening in DRSS (yes/no);				
Proportion of eyes who lose ≥ 5 , ≥ 10 , or ≥ 15 letters in BCVA from baseline by visit over time	Binary endpoints: patients had a BCVA loss \geq 5 (yes/no); patients had a BCVA loss \geq 10 (yes/no); patients had a BCVA loss \geq 15 (yes/no). [Visual Acuity Score/EDC]				
Time to first development of PDR, ASNV, or DME through Week 48	Time to event endpoint: Time from first treatment to development of PDR, ASNV, or DME (in months) [Sight-threatening Complication/EDC]				

Table 4: Additional Secondary Efficacy Endpoints and Analysis Methods

KS301P106 SAP Version 0.1 KSI-301 – Kodiak Sciences Inc.

Additional Secondary Efficacy Endpoint	Variable Derivation [Source]	Summary Statistics [Analysis Set]	Method of Analysis			
Time to first development of PDR or ASNV through Week 48Time to event endpoint: Time from first treatment to development of PDR or ASNV (in months) [Sight-threatening Complication/EDC]						
Time to first development of vitreous hemorrhage or tractional retinal detachment, believed to be due to PDR through Week 48	to first development of us hemorrhage or onal retinal detachment, red to be due to PDR gh Week 48		Kaplan-Meier and Cox regression model stratified by randomization stratification factors (Section 7.3)			

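### SAP 7.3 leaves eyes diagnosed with PDR before Week 48 without a usable Week 48 DRSS grade, so the DRSS-worsening endpoints miss eyes they are meant to count

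*SAP*

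**What the plan says.** SAP 7.3 sets one rule for every endpoint in the additional secondary group: "data after the occurrence of intercurrent event will be censored, and missing and non-gradable data will not be imputed". The analysis then rests on data that were seen, could be graded and were not censored. SAP Table 4 includes among these endpoints the proportions of eyes with at least 2-step and at least 3-step "worsening on DRSS from baseline at Week 48".

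SAP 7.3 does not say which intercurrent events it means. The full list is in SAP 7.1.1.4, and its third item is "Development of sight-threatening complication(s) and initiation of open-label KSI-301 5 mg treatment, panretinal photocoagulation, or other treatment for DME, ASNV, and/or PDR". SAP 7.2.1 has a shorter list, introduced by "The following intercurrent events will be evaluated in this key secondary endpoint", which leaves out sight-threatening complications.

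For the primary endpoint, SAP 7.1.2 says that "measurements after occurrence of intercurrent event will be imputed using the last observation carry forward (LOCF) procedure". SAP 7.2.2 applies the same method to 3-step improvement.

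On the denominator, SAP 5.1 says that by default "the denominator to determine the percentage of subjects in each category will be based on the number of subjects with available data". SAP 7.1.2, which Table 4 cites as similar, divides by the "number of patients in FAS".

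Protocol 4.1.3.1 requires a fundus photograph at the diagnosis (Dx) visit and says it will feed the DRSS endpoint assessment. Protocol 9.4.3 uses LOCF for secondary endpoints and censors only the DRSS scores collected after the complication. SAP 1.0 promises that changes from the protocol "will be described and explained in Section 10.0".

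**The concern.** Worsening on this scale and developing PDR are largely the same event in this population. A rule that discards data after treated PDR, and carries nothing forward, discards the outcome itself. This is not ordinary missing data, because an eye's grade is lost as a result of its getting worse.

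The same SAP carries the last grade forward for improvement but not for worsening, although both are read from the same photographs. The protocol carries it forward for both.

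At stake is the reported Week 48 difference in worsening and its 95% confidence interval. The proportions would be too low. If more sham than KSI-301 eyes develop PDR, the comparison would also be pulled toward no difference.

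A related gap concerns the incidence and time-to-event endpoints for PDR or ASNV, for vitreous hemorrhage or tractional detachment, and for DME. SAP 7.3 does not say whether the shorter 7.2.1 list applies to them. It is therefore unclear whether, for example, PDR counts in an eye that was first diagnosed with DME.

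**Working it through.** The plan gives no rate, power or sample size for DRSS worsening, so there is no figure to reproduce. The check traces the rule and then illustrates its size.

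1. **Which grades count as worsening.** Eligible eyes are at level 47 or 53 (protocol 5.1.1). The next levels in protocol Table 1 are 60, 61 and 65. If each listed level is one step, two steps lead from 47 to 60 and from 53 to 61. If level 60 (laser scars) is skipped, they lead to 61 and 65. Either way the eye is at level 60 or above. Level 60 also follows a complication: prior PRP is an exclusion (protocol 5.2.1), and protocol 6.8.1 permits it in the study eye if PDR or ASNV develops.

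2. **Whether a Dx-visit grade can reach Week 48.** In SAP Table 3, Week 44 is day 308 and the Week 48 window is days 323 to 364. With the ±14-day visit window, the latest Week 44 visit is 308 + 14 = day 322, so a Dx grade from an in-window scheduled visit up to Week 44 falls outside the Week 48 window. A later photograph does exist. SoA-B places one on day 336 in each case:
   - Dx at Week 8: 56 + 40×7 = 336
   - Dx at Week 20: 140 + 28×7 = 336
   - Dx at Week 32: 224 + 16×7 = 336
   - Dx at Week 44: 308 + 4×7 = 336

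   Open-label treatment starts at the Dx visit (SAP 3.1), so that photograph comes after the intercurrent event and is censored. Without carry-forward the eye has no Week 48 grade.

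3. **Denominator.** With available data (SAP 5.1) the eye drops out. With the FAS (SAP 7.1.2) it counts as not worsened. On neither reading does it count as worsened.

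4. **Illustration; all rates are assumed.** Let p be the true worsening proportion and f the share of worsened eyes first diagnosed at Week 48. Take 120 eyes per arm (SAP 9.0), with p = 0.20 on sham and 0.05 on KSI-301. Carrying the Dx grade forward gives 20% − 5% = 15 points. Under SAP 7.3:
   - available-data proportion = p·f / (1 − p(1 − f))
   - FAS proportion = p·f
   - worsened eyes lost = 120·p·(1 − f)

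   The values of f are 4/48 (constant hazard), 0.30, and 28/48 (PDR found only at the Year 1 angiography visits, Weeks 20 and 48).

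| f | Available data, sham vs KSI-301 | Difference (points) | FAS, sham vs KSI-301 | Difference (points) | Eyes lost, sham vs KSI-301 |
|---|---|---|---|---|---|
| 4/48 | 2.04% vs 0.44% | 1.60 | 1.67% vs 0.42% | 1.25 | 22.0 vs 5.5 |
| 0.30 | 6.98% vs 1.55% | 5.42 | 6.00% vs 1.50% | 4.50 | 16.8 vs 4.2 |
| 28/48 | 12.73% vs 2.98% | 9.75 | 11.67% vs 2.92% | 8.75 | 10.0 vs 2.5 |

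   The first sham entry, for example, is 0.20×(4/48) / (1 − 0.20×44/48) = 0.01667/0.81667 = 2.04%. With 10% vs 3%, the 7-point difference becomes 0.66, 2.31 or 4.31 (available data). With 30% vs 10%, 20 points becomes 2.53, 8.17 or 13.91.

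5. **Limiting case.** Suppose that all PDR is diagnosed before Week 48, that every PDR eye has worsened, and that 2% of other eyes worsen. With PDR in 10% vs 2%, carry-forward gives 11.8% vs 4.0%, a difference of 7.8 points. With 30% vs 5% it gives 31.4% vs 6.9%, or 24.5 points. Under SAP 7.3 with available data, both become 2.0% vs 2.0%, a difference of zero.

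**The case against.** The strongest reply is that SAP 7.3 never says the 7.1.1.4 list applies, and that a shorter list without complications exists. That is correct, so the finding depends on a reading. It is the natural one: 7.1.1.4 is the only list the SAP applies to a DRSS endpoint (7.2.2 refers to it), and protocol 9.4.3 itself censors DRSS after the complication. If another list was intended, the SAP still has to say so.

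The investigator diagnoses PDR while the reading center grades DRSS, and no agreement rate is given. Eyes graded as PDR but never diagnosed keep their Week 48 grade. So do eyes whose Dx visit falls in days 323 to 364, and FAS eyes with a baseline below 47 can worsen without PDR. Nor need every diagnosed PDR be a 2-step worsening. These points limit the size, not the mechanism.

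The illustration removes only worsened eyes. Eyes with DME, or with another intercurrent event, would also leave the available-data denominator. The 28/48 scenario is a favorable bound, since photographs and dilated examinations occur at every scheduled visit from Week 8.

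The closing sentence of 7.3 favors the available-data denominator, so the FAS reading is the weaker one. SAP 10.0 does say that its strategies for intercurrent events and missing data take precedence, but it neither names nor explains this change.

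Finally, the consequence is limited. These endpoints lie outside the 4.98% test family, and the first and third key secondary endpoints still count PDR events. That stands, and it is why this is a correction to make rather than a threat to the trial's main conclusion.

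**Conclusion.** The concern holds. On the 7.1.1.4 list, an eye diagnosed with PDR at a scheduled visit before Week 48 cannot count as worsened at Week 48 under either denominator. This reverses protocol 4.1.3.1 and 9.4.3 and treats worsening opposite to improvement, without the explanation that SAP 1.0 promises.

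That the worsening proportions are understated follows from the rule. The size does not, because every rate used is assumed. Under the three timing scenarios, 1 − f gives a loss of 92%, 70% or 42% of worsened eyes. Bias toward no difference also requires more PDR on sham than on KSI-301, which is expected but not quantified in the documents. Confidence is high for the mechanism. The change should be made before the Week 48 analysis.

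**What to change.** 1. In SAP 7.3, for at least 2-step and at least 3-step DRSS worsening at Week 48, carry forward the last gradable DRSS up to and including the Dx visit. Use all FAS patients as the denominator. Where no post-baseline grade is usable, carry baseline forward as protocol 9.4.3 does. SAP 7.1.2 treats a non-gradable first open-label visit as no change from baseline, so state explicitly which rule governs that case here.
2. For the PDR or ASNV, vitreous hemorrhage or tractional detachment, and DME incidence and time-to-event endpoints, state that the 7.2.1 list applies, so that an event after a different first complication still counts.
3. Record and explain any remaining departure from protocol 9.4.3 in SAP 10.0.

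The cost is SAP wording only. The Dx-visit photograph is already required and sent to the reading center, so no new data are needed.
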